## 10. Exploratory analyses

The exploratory endpoints for this study and a description of the analysis approach for each endpoint are provided below. Change in intraepidermal nerve fiber density (IENFD) from baseline to Week 12 and Week 24 will be analyzed in a subgroup of approximately 120 patients at selected sites. There are 4 comparisons of interest for this analysis:

- Change from baseline in the IENFD in the group of approximately 60 patients that received ricolinostat for 24 weeks. The change from baseline in IENFD will be assessed at 24 weeks using a t-test to test the null hypothesis that the change from baseline in IENFD is zero.
- Change from baseline in the IENFD in the group of approximately 60 patients that received ricolinostat for 12 weeks. The change from baseline in IENFD will be assessed at 12 weeks using a t-test to test the null hypothesis that the change from baseline in IENFD is zero. .
- The difference in the change from baseline in the IENFD in the Intent-to-Treat population at Week 24. An ANCOVA model with change from baseline as the outcome and baseline value and treatment group will be used to test for a difference in groups.
- Other exploratory endpoints may be identified at the time of analysis of the study data.

## 11. Safety analyses

All safety analyses will be performed using the safety population. Safety and tolerability will be assessed by clinical review of all safety parameters including AEs, laboratory values, and vital signs. The safety analyses will include all results collected from randomization through the end of the study. All safety presentations will be presented by treatment group ( 180µg, 120µg, and placebo).

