## **9.6 Safety Extension (Week 12 to Week 24)**

From Week 12 to Week 24, all patients will receive ricolinostat 120 mg daily. Patients will return to the clinic as outlined in the schedule of events and at each visit procedures specified in the schedule of events for that visit will be performed.

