**3.3. Study treatments**

Both ricolinostat and placebo are liquid formulations to be administered orally in the morning. Each bottle of ricolinostat contains 12 mL of a 10 mg/mL solution. Placebo consists of the same liquid formulation, excluding the active ingredient (i.e., ricolinostat). Bitrex® is used in the placebo formulation to mimic the bitter taste of the active ingredient.

3.3.1. *Active arm*

One bottle of ricolinostat (120 mg in 12 mL) will be taken by mouth daily for approximately 24 weeks, which includes an approximately 12-week double-blind, placebo-controlled treatment period and an approximately 12-week open label safety extension period. Kits will be assembled and labeled so that active and placebo supplies are indistinguishable; a single randomization code will be used for each patient.

3.3.2. *Placebo arm*

One bottle of placebo (12 mL) will be taken by mouth each morning daily during the pain observation period and active treatment phase of the study.

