## 5. **Database lock and unblinding**

### 5.1. **Blinded data review (BDR) review of selected data prior to database lock**

The clinical database will undergo a “soft lock” when the last patient that is still in the randomized control period has completed their Week 12 visit or early study discontinuation. During the soft lock, all variables will be locked for changes except for those variables that will continue collection during the 12-week open label period (e.g., adverse events, laboratory assessments, IENFD, etc.); the data from these variables will be locked for all records collected

prior to and through the Week 12 visit. To avoid inadvertent unblinding, any data collected after Week 12 during the open label period will remain unlocked, excluded from analysis, and blinded with respect to treatment group assignment.

After the soft lock and prior to accessing the randomized treatment assignments, a review of locked blinded data will occur to accomplish the following objectives: 1) assess the impact of missing data on study analysis, 2) assess and correct the database for inconsistent data, 3) identify the per-protocol population and, 3) finalize the methods needed for analysis of the study objectives while still blinded to results. Outputs consisting of tables, listing, and figures without treatment groups or with randomly generated treatment group assignments will be produced, as needed, to accomplish the blinded data review.

A second (unblinded) data review may occur after the final patient has completed the Week 28 visit or early study discontinuation. The data collected after the initial soft lock will be analyzed during the second data review. The procedures and objectives for this data review are the same as those described above after study completion of the randomized control period.

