## **5.2. Database lock**

After completion of all BDR procedures, validation of the project databases and Regency's approval of the BDR, the clinical database will be locked. After the database lock and the authorization for unblinding, the treatment codes will be merged to the analysis datasets. After database lock, final endpoint analysis may commence. Note that there will be two separate database locks that follow soft locks and data reviews; one after the randomized control period has completed and one after the Week 28 follow-up period has completed.

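### SAP Section 11 does not separate the double-blind period from the open-label extension, so end-of-study adverse event tables by arm would count ricolinostat-onset events under placebo

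*SAP*

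**What the plan says.** SAP Section 11 sets three rules. On population: "All safety analyses will be performed using the safety population". On span: "The safety analyses will include all results collected from randomization through the end of the study". On layout: "All safety presentations will be presented by treatment group". SAP 11.1 then lists frequency tables by treatment group, including special-interest events and AEs leading to discontinuation. Protocol 10.3.7 asks for AE counts by treatment arm in the Safety Population.

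The treatment that patients take changes partway through that span. Protocol 9.6: "From Week 12 to Week 24, all patients will receive ricolinostat 120 mg daily".

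SAP 5.1 protects the first analysis: "any data collected after Week 12 during the open label period will remain unlocked, excluded from analysis". SAP 5.2 adds: "Note that there will be two separate database locks that follow soft locks and data reviews". One lock follows the randomized period and the other follows Week 28. Section 5.1 says that data gathered after the first soft lock are analyzed at the second review.

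SAP 6.1.5.4 dates an AE with a missing start month or year to the day of randomization. SAP Section 1 makes the SAP govern where it and the protocol differ.

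**The concern.** From Week 12 a patient randomized to placebo is taking the study drug. A cumulative AE table by randomized arm would list under placebo any event that this patient first has on ricolinostat. Read alone, such a table shows the arms closer together than they were under randomized treatment, most of all for events that appear soon after first exposure.

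The primary objective in SAP 2.1 includes safety against placebo, and Protocol 7.2 gives further safety assessment as the purpose of the extension. A mixed table serves neither aim. The special-interest and discontinuation tables are exposed in the same way.

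**Working it through.** **Is there an assignment rule anywhere?** I looked where one would sit.

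- Treatment-emergent definition (SAP 4.4.1): begins at the start of study drug, with no end and no reset at the switch.
- Safety population (SAP 6.1.2): randomized and dosed, with no as-treated or period rule.
- AE table list (SAP 11.1) and Protocol 10.3.7: by group or arm, with no period.
- Locks (SAP 5.1, 5.2): fix when data are analyzed, not the column in which an event is counted.
- Biopsy endpoint (SAP 4.3.4): notes that placebo patients will have had 12 weeks of ricolinostat, but for nerve fiber density only.

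The group labels in Section 11 do not fill the gap. They name 180 µg, 120 µg and placebo, whereas SAP 3.3 describes two arms, placebo and ricolinostat 120 mg.

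**Arm size.** The plan assumes a difference of 0.8, SD 2.35, two-sided 0.05 and 80% power. Per arm, n = 2 × (1.960 + 0.842)² × (2.35/0.8)² ≈ 135.5, so 136 per arm and 272 in total, against about 274 stated. The figure reproduces. I use 137 per arm below only to turn percentages into patients.

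**Exposure, from the documents.** For a placebo-arm completer, 12 of 24 treatment weeks are on ricolinostat. Of the 28 weeks after randomization, 16 follow the switch (57%): 12 on ricolinostat (43%) and 4 off drug.

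**Illustration.** The documents give no AE rates and plan no AE test, so every risk here is an assumption. Let b and d be the 12-week risks on placebo and drug, and f the fraction entering the extension, independent of earlier events. To Week 24:

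- Placebo arm: b + (1 − b)·f·d
- Drug arm, constant risk: d + (1 − d)·f·d, so the difference is (d − b)(1 − f·d)
- Drug arm, excess only at first exposure: d + (1 − d)·f·b, so the difference is (d − b)(1 − f)

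With b = 0.05 and d = 0.15:

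| | Placebo arm | Drug arm | Difference (points) | Risk ratio |
|---|---|---|---|---|
| Double-blind period | 5.0% | 15.0% | 10.0 | 3.0 |
| Constant risk, f = 1 | 19.25% | 27.75% | 8.5 | 1.44 |
| Constant risk, f = 0.7 | 14.98% | 23.93% | 8.95 | 1.60 |
| First exposure only, f = 1 | 19.25% | 19.25% | 0 | 1.00 |
| First exposure only, f = 0.7 | 14.98% | 17.98% | 3.0 | 1.20 |

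Placebo-column patients whose first event came on ricolinostat number 137·(1 − b)·f·d. That is 19.5 of 26.4 (74%) at f = 1 and 13.7 of 20.5 (67%) at f = 0.7.

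Other assumed risks, constant on drug and f = 1: 5%/10% moves the difference from 5 to 4.5 points, 10%/20% from 10 to 8.0, and 20%/35% from 15 to 9.75.

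**Partial dates.** An open-label AE with a missing start month or year is set to the randomization date. It would then fall in the double-blind placebo column even if the tables were split by period. A missing day is set to the first of the month (outside the randomization month), which can do the same in the month of the switch.

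**The case against.** The strongest reply is that the comparison that matters is already protected. The first-lock output stops at Week 12, and Protocol 10.3.2 plans the analysis at that point. What remains is the layout of later descriptive tables. This stands, and it limits the weight of the point. A reader might infer that the placebo-controlled safety comparison is itself contaminated; the documents do not support that.

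Second, Section 5.1 can be read as a separate analysis of post-Week-12 data, and the span in Section 11 could be met by two outputs that together cover the study. This is a fair reading, so a pooled table is an inference and not a stated instruction. But Section 5.1 speaks to timing, and Section 11 still runs from randomization to end of study without a split. Even in a separate table, the column for former placebo patients is undefined.

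Third, assignment by randomized arm is inferred. The statement that "a single randomization code will be used for each patient" belongs to a passage on kit labelling. The sentence "After the database lock and the authorization for unblinding, the treatment codes will be merged to the analysis datasets" does not define the codes by period. Protocol 10.3.7, with counts by treatment arm, is the better support.

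Fourth, the plan reports percentages, not risk ratios. Under constant risk in the 5%/15% case the difference barely moves; the large loss needs the excess to be confined to first exposure. Independence of extension entry from earlier events is also a simplification, since AEs can lead to discontinuation. All of this stands.

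A reader might also infer that every safety summary is affected. Laboratory, vital-sign and ECG summaries by time point are not pooled across the switch. Displays with no stated time point can be.

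**Conclusion.** The point holds for second-lock and end-of-study tables and should be fixed; it does not touch first-lock output. Applied by arm as written, Section 11 places ricolinostat-onset events under placebo, unless Section 5.1 is taken to require a separate post-Week-12 analysis.

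The size cannot be known from the documents. On assumed 12-week risks of 5% and 15% with 70% to 100% entering the extension, a 10-point difference becomes 8.5 to 9.0 points (constant risk) or 0 to 3.0 points (excess only at first exposure). Confidence is high that the rule is missing. It is lower for the amount of distortion, which depends on those assumptions and on which reading the programmers adopt.

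The safety text also contains separate errors that bias nothing but leave conflicting instructions: the group labels, the time points in 11.2, 11.4 and 11.5, the special-interest list in 4.4.1 (neutropenia, listed in Protocol 11.10.2.2, is absent, though such events would still count as treatment-emergent AEs), and footnote c of Exhibit 4.

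**What to change.** Main changes to the SAP:

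- Make the main AE comparison the double-blind period by randomized arm, from first randomized dose to before first open-label dose, with a cross-reference from Section 11 to Section 5.1.
- Report extension and follow-up AEs separately by sequence (placebo-ricolinostat, ricolinostat-ricolinostat), with patients who entered the extension as denominator. State the emergence rule for that table, including events that worsen after the switch.
- Change the partial-date rule in 6.1.5.4 so that open-label events are not moved into the double-blind placebo column.
- Apply the same split to the special-interest and discontinuation tables and to displays with no stated time point: the overall ECG and QT/QTc categories in SAP 11.5, and the special-interest laboratory table in Protocol 10.3.7.

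Separate corrections:

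- Reconcile the Section 11 group labels with the two arms in SAP 3.3.
- Replace the time points in 11.2, 11.4 and 11.5 with the Exhibit 3 visits plus the Day 1 one-hour ECG.
- Reconcile the special-interest list in SAP 4.4.1 with Protocol 11.10.2.2 so that neutropenia enters that table.
- Reconcile Exhibit 4 footnote c (double-blind period ends at Week 8) with footnote d and SAP 3.1.

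The cost is SAP wording and table shells. AE onset dates and daily dosing are already collected. The downside is more safety tables, and smaller denominators in the extension.

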### 11.1. Adverse events

AEs will be coded using the Medical Dictionary for Regulatory Affairs (MedDRA) version 22.0 coding system. Frequency tables will be presented by treatment groups summarizing:

- All treatment-emergent AEs

- All treatment-emergent AEs by severity
- All treatment-emergent AEs  $\geq 3$  in severity
- All treatment-emergent treatment-related AEs
- All ESIs
- All treatment-emergent meeting the pre-specified criteria for serious AEs (SAEs)
- All AEs leading to discontinuation

### **11.2. Clinical laboratory evaluations**

Each laboratory value and change from baseline (when appropriate) will be summarized in tables and figures for hematology, blood chemistry and urinalysis for each treatment at Screening, discharge, and end of study. Boxplots of laboratory values will be provided. Shift tables may also be provided.

### **11.3. Physical examination**

A listing of physical examination findings will be provided by patient.

BMI will be summarized for each treatment group at Screening and is calculated from the patient's height and weight.

### **11.4. Vital signs**

Each resting vital sign observed value and change from baseline (when appropriate) will be summarized for each treatment group at Screening, pre-dose, 30 minutes, 1 hour, 2 hours, 4 hours, 6 hours, 8 hours, and 24 hours post-dose administration. Each orthostatic vital sign observed value and change from baseline (when appropriate) will be summarized for each treatment group at Screening, pre-dose, 2 hours, 4 hours, 8 hours, and 24 hours post-dose administration.

#### **11.6. Concomitant medications**

Concomitant medications will be summarized (n and %) by anatomical therapeutic chemical (ATC) class and preferred term (coded by WHO Drug coding dictionary March 2019) for each treatment group. This table will also include an overall total column.

